## **12 DATA MANAGEMENT**

## 12.1 Source Data

Source documents are where data are first recorded, and from which participants' CRF data are obtained. These include, but are not limited to, hospital records (from which medical history and previous and concurrent medication may be summarised into the CRF), clinical and office charts, laboratory and pharmacy records, diaries, microfiches, radiographs, ICM and CIED reports and correspondence.

CRF entries will be considered source data if the CRF is the site of the original recording (e.g. there is no other written or electronic record of data). All documents will be stored safely in confidential conditions. On all study-specific documents, other than the signed consent, the participant will be referred to by the study participant ID number, not by name.

## 12.2 Access to Data

Direct access will be granted to authorised representatives from the Sponsor and host institution for monitoring and/or audit of the study to ensure compliance with regulations.

Trial Protocol	Version 1.24 /Date: 0326/087/20234
ID-AF Study	IRAS Project number: 268739
Chief Investigator: [name]	- REC Ref. 21/LO/0508 ≪
	Page 20 of 28

# 12.3 Data Recording and Record Keeping

The participants will be identified by a unique trial specific ID number which will be assigned following consent. The trial ID number will be used in both hard-copies and electronic documents. The hard copies (CRF and consent forms) of data will be securely kept in the Research Fellows' Office located in the John Radcliffe Hospital, Level 2 Blue Outpatients.

The key to the trial specific ID number will be maintained on a single document will be kept on a separate folder in the PI's office ([name]). This office only be accessed by authorised personnel via a door-code and it is also located in the John Radcliffe Hospital, Level 2 Blue Outpatients.

The name and any other identifying detail will NOT be included in any trial data electronic file.

The LINQ™ and the Confirm Rx™ only transmit recordings to their company's servers (Carelink™, for Medtronic; Merlin.net™, for Abbott) via their respective smartphone app. ICM recordings can only be accessed on these servers by using the clinician web portal. This is the routine clinical practice in OUH for devices which are one remote monitoring (patients don't have to physically attend hospital for a device interrogation). Smartphone apps from Medtronic and Abbott are already used OUH to transmit information from the devices rather than using home-based monitors. The assigned trial specific ID number will be used to register the device in the Carelink (for Medtronic devices) and Merlin.net (for Abbott devices); thus, no identifiable patient information will be in the servers. Access to these servers is via the clinician web portal is password protected.

Transmission reports will be downloaded from the Medtronic™ and Abbott™ servers and stored in password protect excel spreadsheet that will only be used in OUH trust computers.

Personal data will not be kept more than 3 months following the end of the study. Study data will be kept for a minimum of five years.

# **13 QUALITY ASSURANCE PROCEDURES**

The study may be monitored, or audited in accordance with the current approved protocol, GCP, relevant regulations and standard operating procedures.

# 13.1 Risk assessment

Not applicable

# 13.2 Study monitoring

The study will be monitored via the study amendments and progress reports. If any issues arise the study may be monitored, or audited in accordance with the current approved protocol, ICH GCP, relevant regulation and standard operating procedures.

Not applicable:

## 13.3 Study Committees

This is a small, single-centre study using commonly available devices with minimal patient risk, no oversight committees are required.

## **14 PROTOCOL DEVIATIONS**

A study related deviation is a departure from the ethically approved study protocol or other study document or process (e.g. consent process or administration of study intervention) or from Good Clinical Practice (GCP) or any applicable regulatory requirements. Any deviations from the protocol will be documented in a protocol deviation form and filed in the study master file.

## **15 SERIOUS BREACHES**

A "serious breach" is a breach of the protocol or of the conditions or principles of Good Clinical Practice which is likely to affect to a significant degree –

- (a) the safety or physical or mental integrity of the trial subjects; or
- (b) the scientific value of the research.

In the event that a serious breach is suspected the Sponsor must be contacted within 1 working day. In collaboration with the C.I., the serious breach will be reviewed by the Sponsor and, if appropriate, the Sponsor will report it to the approving REC committee and the relevant NHS host organisation within seven calendar days.

# **16 ETHICAL AND REGULATORY CONSIDERATIONS**

# 16.1 Declaration of Helsinki

The Investigator will ensure that this study is conducted in accordance with the principles of the Declaration of Helsinki.

# 16.2 Guidelines for Good Clinical Practice

The Investigator will ensure that this study is conducted in accordance with relevant regulations and with Good Clinical Practice.

## 16.3 Approvals

Following Sponsor approval, the protocol, informed consent form, participant information sheet will be submitted to an appropriate Research Ethics Committee (REC), and HRA (where required) and host institutions for written approval.

Trial Protocol	Version 1. 2 4 /Date: 0326/087/20234
ID-AF Study	IRAS Project number: 268739
Chief Investigator: [name]	
 
REC Ref: 21/LO/0508
 

-	Page 22 of 28

The Investigator will submit and, where necessary, obtain approval from the above parties for all substantial amendments to the original approved documents.

# 16.4 Reporting

The CI shall submit once a year throughout the study, or on request, an Annual Progress report to the REC Committee, HRA (where required) host organisation, Sponsor and funder (where required). In addition, an End of Study notification and final report will be submitted to the same parties.

# 16.5 Other ethical issues

In the event of a clinically relevant arrhythmia being detected by the ICM but not by the pacemaker, the research team will take steps to quickly inform the subject's clinical team so that if required, it can be promptly acted upon'

# 16.6 Participant Confidentiality

The study will comply with the General Data Protection Regulation (GDPR) and Data Protection Act 2018, which require data to be de-identified as soon as it is practical to do so. The processing of the personal data of participants will be minimised by making use of a unique participant study number only on all study documents and any electronic database, with the exception of the CRF, where participant initials may be added. All documents will be stored securely and only accessible by study staff and authorised personnel. The study staff will safeguard the privacy of participants' personal data.

No identifiable details will be published.

# 16.7 Expenses and Benefits

Reasonable travel expenses for any visits additional to normal care will be reimbursed on production of receipts, or a mileage allowance provided as appropriate.

# **17 FINANCE AND INSURANCE**

# 17.1 Funding

This trial will be partially supported by a grant from Abbott Medical Grant, Medtronic Grant or consumables and Rhythm Management Research Hub.

# 17.2 Insurance

NHS bodies are legally liable for the negligent acts and omissions of their employees. If you are harmed whilst taking part in a clinical research study as a result of negligence on the part of a member of the study team this liability cover would apply.

Non-negligent harm is not covered by the NHS indemnity scheme. The Oxford University Hospitals NHS Foundation Trust, therefore, cannot agree in advance to pay compensation in these circumstances.

In exceptional circumstances an ex-gratia payment may be offered.

# 17.3 Contractual arrangements

Appropriate contractual arrangements will be put in place with all third parties.

## **18 PUBLICATION POLICY**

The Investigators will be involved in reviewing drafts of the manuscripts, abstracts, press releases and any other publications arising from the study.

Authorship will be determined in accordance with the ICMJE guidelines and other contributors will be acknowledged.

# 19 DEVELOPMENT OF A NEW PRODUCT/ PROCESS OR THE GENERATION OF INTELLECTUAL PROPERTY

Ownership of IP generated by employees of the OUH vests in OUH. The protection and exploitation of any new IP is managed by the IP and Research Contracts Team at OUH unless it is generated in collaboration with Oxford University in which case this is led by the University's technology transfer office, Oxford University Innovations.

## 20 ARCHIVING

All documents will be stored securely in Clinical Fellows Research Office in the John Radcliffe Hospitals which requires a code to gain entrance to the office. The documents will only be accessible by study staff and authorised personnel.

The study staff will safeguard the privacy of participants' personal data.

[figure not shown]

## 22 APPENDIX A: STUDY FLOW CHART

# 23 APPENDIX B: SCHEDULE OF STUDY PROCEDURES

Procedures	Number of visits: 3					
	Assessment		Visit 1 (Telephone Clinic)		Final visit	
-	Day 0	Day 0	Day 0	4-6 weeks	2-5 months	6 Months
	Screening	Baseline	Implant		Monthly Remote Downloads	Device interrogation ICM explant
Informed consent	х					
Demographics	х					
Medical history	х			x		
Physical examination	х					
Medications		x		x		
Eligibility assessment	х					
Implant indication		×				
Randomisation		x				
ICM Implant			x			
Device interrogation and programming		X		x	x	x
ICM Explant						х
Adverse event assessments						x

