# 3. SYNOPSIS

Trial Title	Comparison of the performance of Implantable Cardiac Monitors and Cardiac Implantable Electronic Devices in detecting Atrial Fibrillation				
Internal ref. no. (or short title)	ID-AF				
Trial registration	Intended register – Clinicalt	rials.gov			
Sponsor	Oxford University Hospitals	NHS Foundation Trust			
Funder	Cardiac Rhythm Research H Abbott Medical Medtronic	ub (Oxford University Hospital	s)		
Clinical Phase	Pilot study				
Trial Design	Prospective, single centre, r	andomised observational stud	ly.		
Trial Participants		ith a dual-chamber CIED with or Persistent Atrial Fibrillation	a functioning		
Sample Size	30 subjects (15 on each investigation arm)				
Planned Trial Period	15 months Extension of study end date until 30 th June 2024				
Planned Recruitment period	<del>3 – 6 months</del> Extension of recruitment period until 31 st December 2023				
	Objectives	Outcome Measures	Timepoint(s)		
Primary	Primary Objective 1. To compare the performance of the Confirm Rx ™ ICM and Reveal LINQ ™ ICM in detecting clinically significant AF episodes (episodes longer than 6 minutes) to CIED (gold standard).	1. Confirm Rx and Reveal LINQ ™ ICM sensitivity, specificity, positive predictive value and negative predictive value will be calculated for AF episodes longer than 6 minutes	During follow-up (6 months)		
Secondary	Secondary Objectives				
	1. To compare the changes in R-wave amplitude following implantation in both ICMs.	
 
Compared the percentage of changes in R-wave amplitude between both ICMs
 
	1. During the follow- up period (6 month)		
	2. To compare the transmission success rate	
 
The percentage of successful transmission in both ICMs will be calculated.
 
	2. During the follow- up period (6 month)		

	of both devices. 3. To compare between both devices the number of patient- activated recordings that contains symptoms attributed to those episodes.	3. The percentage of activated recordings with symptoms will be calculated.	3. During follow-up period (6 months)
Intervention(s) 
 
Medical Device
 
	Implantable cardiac monito LINQ™(Medtronic)	ors (ICM): Confirm Rx™ (Abbo	tt) and Reveal
Comparator		ectronic Devices (Pacemak Implantable cardioverter-defi	

|

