# 7. STUDY DESIGN

The ID-AF study is a prospective, single centre, randomised observational study aimed at comparing the performance of the Confirm  $Rx^{M}$  and Reveal LINQM ICMs in the detection of clinically relevant atrial fibrillation (AF) episodes to cardiac implantable electronic devices (CIED)

Subjects with pre-existing cardiac implanted electronic devices (Pacemakers, CRT and ICD devices) who have remote monitoring ability and are able to record electrograms will be identified by interrogation of the John Radcliffe Hospital Pacemaker Database. Subjects with a functioning atrial lead, on remote monitoring, non-permanent AF with an AF burden of more >2% in the last year will be invited to participate. Those who have expressed an interest in participating will be invited for an initial interview (eligibility assessment, baseline assessment and informed consent).

[figure not shown]
This study will randomise 30 subjects to receive either a Confirm Rx™ ICM or a Reveal LINQ™ ICM. The ICM will be implanted in the Outpatient setting as a Day Case Procedure according to manufacturer instructions. Prior to the implant, 2 minutes of recording in V1 and V2 position with the surface ICM mapping will be performed. The R-wave amplitude will be recorded at the end of the procedure. Subjects will be taught how to use the home-based transmitter and mobile app.

As it is standard of care, the research team will book a telephone follow-up appointment at 4-6 weeks to address any questions the subjects may have regarding the ICM, review ICM battery and wound. The ICMs are programmed for automatic daily transmissions of the recorded episodes to the Clinician's Web Portal. Scheduled remote transmissions for CIED will be performed at least monthly. At 6 months, subjects will be invited to attend a Device Clinic appointment for the final download from both devices. At this time, they may choose to have the ICM removed or left in-situ but turned off. During this last visit, ICM transmissions log will be interrogated. The end of the study for each patient will be the date of the 6 months follow-up appointment.

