## 7.2 Study Risks

The Confirm Rx™ ICM and the Reveal LINQ™ ICM implant procedure is safe and minimally invasive. They are both have CE marking and having been used in routine clinical practice for several years. The procedure will be performed under sterile conditions and local anaesthetic using the insertion tools supplied by the manufacturer. They have very similar implant techniques and they are both injected subcutaneously in the anterior chest wall.

There are no known contraindications. Potential adverse events include:

- bruising,
- haematoma (<1%),
- superficial infection (<1%),
- keloid formation,
- migration
- extrusion.

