# 8.9.1 Intervention – ICM implant (Confirm Rx™ or Reveal LINQ™)

The Confirm Rx™ ICM or Reveal LINQ™ ICM will be implanted as a Day Case. Prior to implant, recording of surface electrograms will be performed in V1 and V2 position to assess P and R-wave amplitudes. The procedure will be performed under sterile conditions and local anaesthetic (lidocaine 1%) using the insertion tools supplied by the manufacturer. They have very similar implant techniques and they are both injected subcutaneously in the anterior chest wall. If there is suboptimal R wave amplitude the operator can reposition the device. The subject will be premedicated with intravenous antibiotics as per Trust Policy to reduce the risk of infection. The operator may choose to close the wound with steri-strips, glue or a suture.

At the end of the procedure the R-wave amplitude will be recorded. Subjects will be taught how to use the mobile apps or the home-based monitor, depending on the device. They will be able to initiate recordings, send transmission and record their symptoms The CIED will be programmed to record any AT/AF and save the electrogram for future adjudication. The CIED and ILR date and time clocks will be synchronized.

The Confirm Rx™ ICM and the Reveal LINQ™ ICM implant procedure is safe and minimally invasive. There are no known contraindications. Potential adverse events include bruising, haematoma, superficial infection, keloid formation, migration or extrusion.

The LINQ™ and the Confirm Rx™ only transmit recordings to their company's servers (Carelink™, for Medronic; Merlin.net™, for Abbott) via their respective smartphone app or homebased monitor. ICM recordings can only be accessed on these servers by using the clinician web portal. The assigned trial specific ID number will be used to register the device in the Carelink (for Medtronic devices) and Merlin.net (for Abbott devices); thus, no identifiable patient information will be in the servers. Access to these servers is via the clinician web portal is password protected. Transmission reports will be downloaded from the Medtronic™ and Abbott™ servers and stored in password protect excel spreadsheet that will only be used in OUH trust computers.

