# 8.10.2 Visits

Visit 1: As is standard of care, Telephone Clinic review at 4-6 weeks after the ICM implant to review the wound, check performance and battery of ICM.

Visit 2: At 6 months, subjects will attend Device Clinic for a final download of both devices and at this time, they may choose to have the ICM removed. An updated drug history will be recorded.

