# **10.2** Reporting Procedures for Serious Adverse Events

A serious adverse event (SAE) occurring to a participant should be reported to the REC that gave a favourable opinion of the study where in the opinion of the Chief Investigator the event was 'related' (resulted from administration of any of the research procedures) and 'unexpected' in relation to those

procedures. Reports of related and unexpected SAEs should be submitted within 15 working days of the Chief Investigator becoming aware of the event, using the HRA report of serious adverse event form.

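### Appendix B schedules adverse-event assessment only at 6 months, so non-serious implant complications that resolve early, or occur in participants who leave early, may be under-recorded

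*Combined protocol and SAP*

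**What the plan says.** Appendix B has six timed columns: screening, baseline and implant (all Day 0), 4-6 weeks, 2-5 months and 6 months. The row "Adverse event assessments" is marked once, in the last of these.

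Section 8.10.2 describes Visit 1 as a telephone "Clinic review at 4-6 weeks after the ICM implant to review the wound, check performance and battery of ICM". Section 7 describes the same contact: "the research team will book a telephone follow-up appointment at 4-6 weeks to address any questions the subjects may have", with battery and wound also reviewed. For Visit 2, section 8.10.2 says "At 6 months, subjects will attend Device Clinic for a final download of both devices". It adds optional removal of the ICM and an updated drug history, and does not mention adverse events.

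The expected complications are named in section 8.9.1: "Potential adverse events include bruising, haematoma, superficial infection, keloid formation, migration or extrusion". Section 7.2 gives the same list and puts haematoma and superficial infection each below 1%.

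Section 10 defines serious adverse events and sends to the ethics committee those that are both related and unexpected. Such reports "should be submitted within 15 working days of the Chief Investigator becoming aware of the event". It sets no collection period and no recording rule for non-serious events. Section 8.11 arranges follow-up of an adverse event when that event is the reason for withdrawal.

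**The concern.** The plan arranges to look at the wound at 4-6 weeks but does not say that what is found is recorded as an adverse event. The one scheduled assessment comes months later. If bruising, haematoma or superficial infection arise soon after implant and settle, they will usually be over by then. A participant who is lost to follow-up, or who withdraws for a reason other than an adverse event, may never reach that assessment.

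What is at stake is a complete record of the harms of a procedure done for research in people who already carry a CIED. Section 13.1 marks risk assessment as not applicable and section 13.3 provides no oversight committee, so recording at scheduled contacts is the main organised way in which non-serious complications would enter the study data.

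**Working it through.** The protocol states no figure on this point, so there is none to reproduce. The check is mainly a reading of the schedule against the text, with some arithmetic for scale.

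**1. Is the single mark real, or an artefact of reading the table from PDF?** Matching each mark to the header by column position gives:

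| Row in Appendix B | Columns marked |
|---|---|
| Medical history | Screening, 4-6 weeks |
| Medications | Baseline, 4-6 weeks |
| Device interrogation and programming | Baseline, 4-6 weeks, 2-5 months, 6 months |
| ICM explant | 6 months |
| Adverse events | 6 months |

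The adverse-event mark sits in the same position as the explant mark, which sections 7 and 8.10.2 also place at 6 months. Three other rows use the 4-6-week column. The column was available, and the adverse-event row leaves it blank.

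**2. Does another section supply earlier recording?**
- Sections 7 and 8.10.2: the wound is reviewed at 4-6 weeks, with no instruction to record a finding as an adverse event.
- Section 8.9.1 (implant): lists complications, with no recording step.
- Section 8.10.1 (monthly transmissions): device data only.
- Section 8.11: the reason for withdrawal goes in the CRF, and an event causing withdrawal is followed up. This does not reach events in people who stay, or who leave for other reasons.
- Section 10: serious events only.

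None closes the gap for a non-serious complication.

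**3. Time gap** (assumption: 6 months is about 26 weeks).
- Implant to the scheduled assessment: about 26 weeks.
- Wound review to the scheduled assessment: 26 − 6 = 20 weeks to 26 − 4 = 22 weeks.

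**4. Scale.** Inputs: 30 implants, 15 per arm (section 3), and a rate p below 1% for haematoma and for superficial infection (section 7.2). Expected events of one type = n × p. Chance of at least one = 1 − (1 − p)^n, taking participants as independent.

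| p | Expected in 30 | At least one in 30 | At least one in 15 |
|---|---|---|---|
| 0.5% | 30 × 0.005 = 0.15 | 1 − 0.995^30 = 14.0% | 1 − 0.995^15 = 7.2% |
| 1% (upper limit) | 30 × 0.01 = 0.3 | 1 − 0.99^30 = 26.0% | 1 − 0.99^15 = 14.0% |

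For either complication the study will probably see no event. If it sees one, that may be the only one. The documents give no rate for bruising, keloid formation, migration or extrusion, so the total number of events at risk of being missed cannot be calculated.

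**The case against.** The strongest case on the other side is that a blank cell does not mean that nothing is recorded. Appendix B is not a full list: the wound review has no row, and the 6-month drug history in section 8.10.2 is not marked at 6 months. Medical history is marked at 4-6 weeks, which gives a place to note a complication. Section 12.1 names hospital records and clinical charts as source data, so the 6-month assessment can draw on notes made earlier. Section 8.4 says that the research team belongs to the clinical care team, so a complication seen in care may reach it directly. Safety is not an objective or an outcome, the devices are CE-marked, and this is a 30-patient pilot.

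Much of this stands, and it limits the point. It does not remove it: each is a route by which a complication may come to light, and none requires it to be recorded as an adverse event.

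Four stronger readings are tempting, and the documents do not support them.
- *Reports to the ethics committee will be late.* Section 10.2 covers only serious events that are related and unexpected. The complications named above are listed in sections 7.2 and 8.9.1, so they are expected, and most would not be serious under section 10.1. The 15-working-day limit would ordinarily not apply to them. For an unexpected serious event, the duty follows from the Chief Investigator's awareness by any route, not from a visit in Appendix B.
- *The 6-month row is the only capture of safety data.* It is the only scheduled adverse-event assessment. Serious-event reporting, the wound review and the recorded reason for withdrawal also exist.
- *Early complications rest on recall alone.* Records may be used at 6 months. A 4-6-week assessment by telephone would itself lean on the participant's account, though over a much shorter interval.
- *A missed event distorts the comparison of arms, since one event in 15 is 1/15 = 6.7 percentage points.* The arithmetic is right, but sections 6 and 11.2 plan no arm-level rate of adverse events.

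**Conclusion.** The point holds as a gap in recording. Followed as written, the schedule assesses adverse events once, about 26 weeks after implant and 20-22 weeks after the wound review, and no text requires earlier findings to be recorded as adverse events. Non-serious complications that resolve early, or that occur in participants who leave before 6 months for another reason, may be under-recorded.

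The consequence is modest. No primary or secondary outcome is affected. At the stated upper limit, 0.3 haematomas and 0.3 superficial infections are expected in the whole study. What would suffer is the study's description of implant harms, where a single event may be all there is to report.

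The conclusion rests on two assumptions: that the table columns are as read above, which the explant row supports; and that at least some listed complications arise and settle before 6 months. The second is clinically plausible, but the documents give no onset times, and keloid formation and migration may behave differently. The change is worth making because it is nearly free.

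**What to change.** Reconcile Appendix B with section 8.10.2. Mark adverse-event assessment at the implant-day and 4-6-week contacts as well as at 6 months, and enter each event with its onset date in the CRF. One sentence in section 8.10.2 or section 10 should say that complications found at these contacts are recorded as adverse events, whether or not serious. The medications row can be reconciled with the 6-month drug history in the same revision.

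The cost is two marks in a table, one sentence and one CRF line per contact. No visit is added and care does not change. The change does not capture an event that arises after the 4-6-week review in someone who leaves before 6 months, but it covers the period soon after implant, when wound complications would be most likely on the assumption stated above.
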